7.2.8 Treatment as Usual Tracking (TTF) (5 min)

This form is completed by the research staff on a weekly basis during the 12-week treatment phase to capture services received in TAU, including modality and frequency.

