7.3.2 Non-Study Medical and Other Services (NMS) (5-7 min)

Medical resources that are not part of the treatment intervention are primarily recorded on the NMS form. (As noted in Section 9.4.1.1, any services provided at the treatment site will be recorded on a separate tracking form). The NMS form captures services received outside of the study and CTP to include therapy visits, physician visits, residential program detoxification,

hospital detoxification, hospital visits, and emergency room visits and medication use through patient self-report. The assessment also captures health insurance status, employment, internet use, criminal activities, and contact with the criminal justice system. Validity of self-reported heath care utilization has been demonstrated (Wallihan et al., 1999; Roberts et al., 1996; Jay at al., 1994; Harlow & Linet, 1989). The NMS was designed as part of [name] (our collaborating economist's) NIDA funded RO1 "CEA in CTN: BUP/NAL treatment for opioid addicted youth" because the Treatment Services Review (TSR) is not structured for a comprehensive cost analysis of treatment services (French et al., 2000).

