7.3.3 Program DATCAP (30 min)

The program DATCAP is to be completed one time only per site by a program and/or fiscal director at each site, with a separate section completed by each active counselor. This will be completed at about the same time at each site during the trial period about mid-way through overall trial recruitment).

Program-specific costs (including salaries of personnel delivering services, facility costs associated with utilizing TES, counselor hours, and work tasks) will be measured via a modified form of the Program DATCAP (French, Dunlap et al., 1996; 1997). The process for administering the program DATCAP and analyzing the economic cost data are explained in detail within the instrument and User's Manual (French, 2001a; 2001b; www.DATCAP.com), as well as related papers (French et al., 1996; French et al., 1997; French & McGeary, 1997; Salomé & French, 2001).

				Treatment Week												
Measure	Time (min)	S	BL	1	2	3	4	5	6	7	8	9	10	11	12	3/6 Mo F/U
Brief Screen (BSS)	5	х														
Enrollment (ENR-A)	2															
Demographics (DEM)	1		х													
DSM-IV Checklist (DSM)	10		х													
Patient Health Questionnaire (PHQ)	10		х													
MicroCog	15		Х													
Urine Screen (UDS)	5		х	2	2	2	2	2	2	2	2	2	2	2	2	х
Alcohol Screen (ABS)	3		х	2	2	2	2	2	2	2	2	2	2	2	2	х
TLFB (TLFB Summary Form	10		х	х	х	х	х	х	х	х	х	х	х	х	х	х
Risk Behavior	5		Х				Х				Х				Х	х

Assessment Schedule

Assessment Schedule

				Trea	atmen	t Wee	k									
Survey (RBS)																
SAS-SR (SAS)	10		Х												Х	х
Brief Symptom Inventory (BSI)	3	Π	Х				х				х				х	х
Coping Strategies Scale (CSS)	4		х												x	x
Randomization (ENR-B)	RA	Π	Х													
Participant Feedback (PFB)	5						x				x				x	
EuroQol (QOL)	3		Х				Х				Х				Х	х
NMS Non- Study Medical and Other Services (NMS)	7		x				x				x				x	x
TAU Tracking (TTF)	RA	Π		х	х	х	х	x	х	x	х	х	х	х	х	
Program DATCAP (PDC)	30	Sing	gle A	dmin	istrati	on (h	alf wa	y thro	ough s	study	recrui	tment	:)	8	•	

NOTE. S=Screening, BL=Baseline, F/U=Follow Up

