14.14 Economic Analyses

We estimate and analyze incremental cost-effectiveness ratios (ICER) to inform an adoption decision from a health care sector perspective and the treatment program's perspective. The primary ICER will be the incremental costs per increased abstinence time (the clinical measure of effectiveness) and the secondary ICER will be incremental costs per increased quality adjusted life year (QALY) (the economic measure of effectiveness). We distinguish the health care perspective from the CTP perspective by the costs included in the cost-effectiveness ratio. The health care sector perspective include all medical and treatment costs regardless of the setting in which they are incurred. The CTP perspective only includes those costs that are incurred during the substance abuse treatment received within the CTP. All ICERs are assessed over 3 months and over 6 months. There are also two separate exploratory economic analyses. We assess the benefit of reduced criminal activity and use of the criminal justice system and we assess the fixed costs of program startup.

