14.14.3 Estimate Incremental Cost-Effectiveness Ratio

The primary ICER is estimated as the difference between mean costs of the modified TAU + TES group and the mean costs of the TAU group divided by the mean abstinence weeks of the modified TAU+TES group and the mean abstinence weeks of the TAU group. This ratio represents the additional cost of the experimental arm over TAU necessary to produce an additional drug-free week. We will estimate this ratio for both treatment costs and all medical costs. Similarly, a cost-effectiveness ratio will be estimated using QALYs in the denominator. We will estimate the cost-effectiveness ratios at 12 weeks and at 6 months. In total we will have

8 outcomes with the 4 outcomes using abstinence weeks as the denominator as the primary economic outcomes.

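### CTP services are not scheduled to be counted after week 12, so the cost-effectiveness ratios that run past week 12 would contain no later CTP cost

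*Protocol*

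**What the plan says.** Three forms bear on cost.

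- **TTF (7.2.8).** It is "completed by the research staff on a weekly basis during the 12-week treatment phase to capture services received in TAU". The assessment schedule agrees: the "TAU Tracking (TTF" row is marked for weeks 1 to 12 and has no mark at the 3- and 6-month follow-ups.
- **NMS (7.3.2).** This form continues to both follow-ups, but its scope is limited: "The NMS form captures services received outside of the study and CTP to include therapy visits". The same section says that "any services provided at the treatment site will be recorded on a separate tracking form".
- **Program DATCAP (7.3.3).** "The program DATCAP is to be completed one time only per site". It supplies prices, not counts of what each participant used.

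Section 14.14.1(a) takes resource counts from study-site clinical forms and the NMS, and names no other source.

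The economic plan reaches past week 12. Section 14.14.3 says "We will estimate the cost-effectiveness ratios at 12 weeks and at 6 months", with eight outcomes in all. Section 14.14 gives the horizons as 3 and 6 months. The secondary hypothesis in 14.1.2 places them at the 3- and 6-month follow-ups, which 4.2 and 5.2 count from the end of the intervention. On content, section 14.14 says "The CTP perspective only includes those costs that are incurred during the substance abuse treatment received within the CTP", while the health-sector perspective is to include every medical and treatment cost wherever it arises.

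**The concern.** A participant who attends the CTP in week 13 or later generates a cost that no scheduled form records. A CTP-perspective ICER consists only of CTP costs, so its numerator at 6 months would equal its numerator at 12 weeks. A health-sector ICER at 6 months would count a therapy visit elsewhere, through the NMS, but not the same visit at the CTP. That departs from its own definition and treats leavers and stayers differently.

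The gap lies in data collection, so an analysis plan cannot close it. Inverse probability weighting for censored costs (14.14.1(b)) and the sensitivity analysis on attrition of cost data (14.14.5) both need some participants with observed CTP costs in the later period. Here there would be none. The economic analysis is secondary, but the protocol presents it as important for decisions on adoption.

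**Working it through.** **1. Forms against horizons.** Two cost perspectives, two denominators and two time points make the eight ICERs of 14.14.3. Four end at 12 weeks, when the TTF is still running, and are complete. Four are at 6 months and lack CTP counts after week 12; two of these take the CTP perspective. If the wording of 14.1.2 governs, both horizons fall after week 12 and all eight are affected. The power statement in 14.14.4 is set at week 12, so this gap does not touch it.

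**2. The protocol's own inputs.** Section 14.14.4 assumes $467 for TAU and $823 for TAU+TES over 12 weeks. The second figure reproduces: 467 × 1.42 (greater retention) × 0.80 (reduced TAU) + 293 (incentive payout) = $823.5. The incremental cost is 823 − 467 = $356. Section 14.4.2 assumes retention at week 12 of 50% (TAU+TES) and 35% (TAU). Its power also reproduces: hazard ratio 1.515, events 250 × 0.50 + 250 × 0.65 = 287.5, two-sided α = 0.025, power 89.9% against the stated 90%.

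**3. Illustration of the uncounted cost.** The protocol gives no CTP use after week 12, so everything in this step is assumption.

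- Constant hazards to week 12: λ(TAU) = −ln(0.35)/12 = 0.0875 per week; λ(TAU+TES) = −ln(0.50)/12 = 0.0578.
- Mean TAU weeks in treatment: (1 − 0.35)/0.0875 = 7.43. Cost per retained week: 467/7.43 = $62.85.
- Time after week 12: T = 14 weeks (6 months from randomization) or 26 weeks (6 months after the intervention).
- CTP weeks per randomized participant after week 12: S × T with no further drop-out, or S(1 − e^(−λT))/λ with continuing drop-out, where S is retention at week 12.
- A retained TAU+TES week costs either the same as a TAU week or 80% of it, the latter if the 20% reduction persists.

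Uncounted cost, TAU+TES minus TAU, per participant:

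| Drop-out after week 12 | TAU+TES weekly cost | T = 14 | T = 26 |
|---|---|---|---|
| None | 100% | $132 | $245 |
| None | 80% | $44 | $82 |
| Each arm's own hazard | 100% | $124 | $197 |
| Each arm's own hazard | 80% | $64 | $113 |
| TAU hazard in both arms | 100% | $76 | $97 |
| TAU hazard in both arms | 80% | $25 | $32 |

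Highest: (0.50 − 0.35) × 26 = 3.9 weeks × $62.85 = $245. Lowest: TAU has 2.83 weeks; TAU+TES has 4.04 weeks × 0.80 = 3.23; the difference of 0.40 × $62.85 is $25.

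**4. Scale.** Relative to the assumed $356, the range is 25/356 = 7% to 245/356 = 69%. As a share of the incremental cost once the missing part is added, it is 25/381 = 7% to 245/601 = 41%. The second pair is the understatement in the usual sense.

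**5. What removes or reverses it.** If CTP care ends at week 12 for everyone, the difference is zero. With the same further drop-out in both arms, it reverses if a retained TAU+TES week costs less than 0.35/0.50 = 70% of a TAU week.

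**The case against.** The strongest reply is that little CTP care may remain to be counted. Section 5.2 explains the 12-week period as reflecting the usual length of an episode in these programs, so many participants retained at week 12 may be finishing. This stands as a limit on size. It does not close the gap, because the planned episode in 6.1 and the attendance requirement in 6.5(b) are both minimum lengths, and nothing in the protocol ends CTP care at week 12.

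A second reply is that the data exist. Under 6.5(h) each CTP must be able to supply attendance records for all participants, and section 10.0 has staff obtain them with session durations, with no stated end date. The counts are therefore potentially recoverable, and it would be too strong to infer that the follow-up hypothesis cannot be answered. But section 10.0 documents these records on the tracking form, and no abstraction is scheduled after week 12.

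A third reply concerns direction. A reader might infer that the later ICERs are bound to favour TAU+TES because more of that arm is retained. The documents do not support this as a fact. Retention at week 12 is not CTP use afterwards, and the larger group of TAU drop-outs (65% versus 50%) could re-enter the CTP, which would put missed cost in the TAU arm. This objection stands.

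**Conclusion.** The collection gap is established from the text. CTP services are counted only in weeks 1 to 12, the follow-up cost form excludes them, and at least four planned ICERs run beyond that point. Those ICERs would not measure what section 14.14 defines.

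A reader might extend this to all the ICERs. Under 14.14.3 that is wrong, since the four at 12 weeks are complete; it would hold only under the follow-up wording of 14.1.2.

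The size and direction of the error are unknown. The range of $25 to $245 per participant, larger in TAU+TES, rests on three assumptions: that those retained at week 12 continue in CTP care, that the 12-week TAU cost spread over retained weeks is a fair weekly price, and that re-entry after drop-out is negligible. The upper end also needs the longer horizon, no further drop-out and no lasting reduction in TAU cost. Neither co-primary endpoint is affected. The point is worth settling before follow-up begins.

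**What to change.** Preferred: abstract CTP attendance records onto the TTF through the last ICER horizon for all participants in both arms, amend 7.2.8 accordingly, and mark the TTF in the 3- and 6-month column of the assessment schedule. The cost is modest record abstraction at two further time points, from records that sites must already be able to supply.

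Otherwise: limit the CTP-perspective ICERs to 12 weeks, and state that health-sector ICERs beyond 12 weeks exclude CTP care. This costs only wording, but gives up the CTP-perspective part of the follow-up hypothesis.

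In either case, state one set of ICER horizons, with their time origin, in 14.1.2, 14.14 and 14.14.3, so that it is clear which ratios run past week 12.

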7.3 Planned Assessments for Economic Analyses

The following assessments will be used to obtain data needed for the planned economic analyses:

7.3.1 EuroQol EQ5D (QOL) (3 min) (the EuroQol Group, 1990; Dolan, 1997)

The EuroQol instrument is a standardized general (not disease-specific) system for describing and valuing health-related quality of life. The instrument consists of two components: the EuroQol classification instrument, which describes the respondent's health within 5 domains, and a visual analog scale, with which respondents rate their health. Responses to each component yield a preference weight that can be used to construct Quality-Adjusted Life Year estimates (QALYs).

7.3.2 Non-Study Medical and Other Services (NMS) (5-7 min)

Medical resources that are not part of the treatment intervention are primarily recorded on the NMS form. (As noted in Section 9.4.1.1, any services provided at the treatment site will be recorded on a separate tracking form). The NMS form captures services received outside of the study and CTP to include therapy visits, physician visits, residential program detoxification,

hospital detoxification, hospital visits, and emergency room visits and medication use through patient self-report. The assessment also captures health insurance status, employment, internet use, criminal activities, and contact with the criminal justice system. Validity of self-reported heath care utilization has been demonstrated (Wallihan et al., 1999; Roberts et al., 1996; Jay at al., 1994; Harlow & Linet, 1989). The NMS was designed as part of [name] (our collaborating economist's) NIDA funded RO1 "CEA in CTN: BUP/NAL treatment for opioid addicted youth" because the Treatment Services Review (TSR) is not structured for a comprehensive cost analysis of treatment services (French et al., 2000).

7.3.3 Program DATCAP (30 min)

The program DATCAP is to be completed one time only per site by a program and/or fiscal director at each site, with a separate section completed by each active counselor. This will be completed at about the same time at each site during the trial period about mid-way through overall trial recruitment).

Program-specific costs (including salaries of personnel delivering services, facility costs associated with utilizing TES, counselor hours, and work tasks) will be measured via a modified form of the Program DATCAP (French, Dunlap et al., 1996; 1997). The process for administering the program DATCAP and analyzing the economic cost data are explained in detail within the instrument and User's Manual (French, 2001a; 2001b; www.DATCAP.com), as well as related papers (French et al., 1996; French et al., 1997; French & McGeary, 1997; Salomé & French, 2001).

				Treatment Week												
Measure	Time (min)	S	BL	1	2	3	4	5	6	7	8	9	10	11	12	3/6 Mo F/U
Brief Screen (BSS)	5	х														
Enrollment (ENR-A)	2															
Demographics (DEM)	1		х													
DSM-IV Checklist (DSM)	10		х													
Patient Health Questionnaire (PHQ)	10		х													
MicroCog	15		Х													
Urine Screen (UDS)	5		х	2	2	2	2	2	2	2	2	2	2	2	2	х
Alcohol Screen (ABS)	3		х	2	2	2	2	2	2	2	2	2	2	2	2	х
TLFB (TLFB Summary Form	10		х	х	х	х	х	х	х	х	х	х	х	х	х	х
Risk Behavior	5		Х				Х				Х				Х	х

Assessment Schedule

Assessment Schedule

				Trea	atmen	t Wee	k									
Survey (RBS)																
SAS-SR (SAS)	10		Х												Х	х
Brief Symptom Inventory (BSI)	3	Π	Х				х				х				х	х
Coping Strategies Scale (CSS)	4		х												x	x
Randomization (ENR-B)	RA	Π	Х													
Participant Feedback (PFB)	5						x				x				x	
EuroQol (QOL)	3		Х				Х				Х				Х	х
NMS Non- Study Medical and Other Services (NMS)	7		x				x				x				x	x
TAU Tracking (TTF)	RA	Π		х	х	х	х	x	х	x	х	х	х	х	х	
Program DATCAP (PDC)	30	Sing	gle A	dmin	istrati	on (h	alf wa	y thro	ough s	study	recrui	tment	:)	8	•	

NOTE. S=Screening, BL=Baseline, F/U=Follow Up

8.0 OUTCOME MEASURES

8.1 **Primary Outcome Measures**

This study will include two primary outcome measures. The first primary outcome will be a measure of abstinence and we hypothesize that the modified TAU+TES intervention will promote significantly greater drug and heavy alcohol use abstinence compared to the TAU arm during the 12 weeks of treatment. Specifically, we will use longitudinal, piecewise, logistic regression to model all 12 weeks, but test for a treatment difference only during the last 4 weeks of the treatment phase. This first primary outcome measure will use half-weeks of abstinence from all tested drugs of abuse and heavy drinking (i.e., 5 or more drinks per day for men and 4 or more for women) during the 12 weeks of treatment, as confirmed via urine toxicology results measured twice weekly and self-reported use assessed via the TimeLine Follow-Back (completed weekly). Thus, the primary outcome measure will depend on urine-confirmed self report of drug use and self report of heavy drinking days. Participants will be considered negative from all drugs and heavy drinking days if both urine and self-report data reflect the absence of drug/alcohol use. Drug use will be evaluated by considering the following stratification variables as covariates: testing drug positive or negative at baseline and primary drug of use as a stimulant or non stimulant. Primary analyses will be conducted to model the effects observed during the intervention period; and separate analyses will be conducted to examine the durability of effects during the post-intervention follow-up period.

The second primary outcome is a measure of retention. We hypothesize that the modified TAU+TES intervention will promote significantly greater treatment retention relative to TAU during the 12-week treatment phase. The measure of treatment retention will be the number of days participants are in treatment (time until last face-to-face contact). As previously discussed, we have included both drug abstinence and retention as primary outcome measures in this trial, as drug abstinence is the primary goal of the planned treatment interventions and retention is typically quite low in the target population and is a clinically significant outcome that is strongly predictive of drug abstinence. Based on prior work with TES (Bickel, Marsch et al., 2008) and the prior CTN trials using non-computerized contingency management interventions with a similar population (MIEDAR CTN protocols # 006 & 007, published in Petry et al., 2005a), we expect that the modified TAU+TES intervention to be evaluated in this trial will positively impact both drug abstinence and treatment retention relative to TAU.

8.2 Secondary Outcome Measures

We will also evaluate secondary outcomes of (a) HIV risk behavior (using the Risk Behaviors Survey; Booth et al., 1993), (b) Psychosocial functioning in areas of criminal activity, health status improvement, psychological status, family/social relationships, and employment (via the SAS-SR, Weissman, 1999; NMS, and BSI, Derogatis & Melisaratos, 1983), and (c) treatment acceptability measured via the Participant Feedback Survey (which we have successfully used in prior trials).

9.0 STUDY PROCEDURES

9.1 Informed Consent Procedures

Informed consent procedures must be conducted within 30 days of the date that participants entered the CTP for a new treatment episode. Every effort will be made to conduct consent procedures as soon as possible after a patient enters a CTP for a new treatment episode; however, a 30-day window allows for a broader array of eligible patients to be considered for study participation. As part of the informed consent procedure, the schedule for earning incentives for drug negative urines and alcohol breath tests and for completion of TES modules will be presented to and discussed with the participant.

9.2 Baseline Assessment

After signing Informed Consent, participants will be asked to complete the baseline assessments (including the urine sample and breath alcohol collection), as described in Section 8 above. We expect that participants will complete Informed Consent and baseline assessments in the same day. If s/he does not finish the Informed Consent and baseline assessments in one day, s/he will asked to return as soon as possible (and preferably the following day but within the eligibility window of one month post treatment intake) to finish the baseline assessment. In this case, another urine and breath alcohol sample will be collected at the subsequent visit and the day that the intake is completed will be counted as the study intake day.

9.3 Randomization

After providing Informed Consent and completing the baseline assessment, participants will be randomly assigned to either (1) TAU or (2) modified TAU that incorporates the computerized intervention and incentives (TAU+TES). The randomization is used to provide balance with respect to measured and unmeasured patient characteristics across the randomized treatment arms. Randomization will be stratified on (1) site, (2) participants' primary substance of abuse (dichotomized as stimulant vs. non-stimulant) and (3) whether one is drug-positive/negative at baseline (based on urine/breath screens). The randomization procedure will be conducted in a centralized process through the CTN Data and Statistics Center 2 (DSC 2). The randomization sequence will be unknown to staff, but group assignment will not be masked after randomization. The DSC 2 statistician will generate the randomization scheme for the study. The randomization schedules will consist of balanced blocks within strata to ensure relative equality of assignment across treatment groups. The block sizes will be varied and randomly permuted to further prevent the potential for guessing the next assignment, which is heightened when a fixed block-size is used. The block size will not be revealed to participating investigators and will be randomly selected from a small number of different block sizes to help reduce the likelihood of an investigator predicting the next treatment assignment. This scheme will provide chronological balance during patient enrollment with respect to the number of patients allocated to each treatment arm, and will thus balance the treatment groups with respect to possible changes in the mix of patients over time. The DSC 2 statistician will review the randomization data on a regular basis to ensure that the scheme is being implemented according to plan. The randomization slot will not be re-allocated to a new patient due to the intent-to-treat nature of the study.

